#### Exploratory objectives

Exploratory efficacy variables include the:

- PEBEQ Multi-Item Event Specific Subscale Total
- PEBEQ Multi-Item General Subscale Total

A linear mixed effects model will be used to evaluate treatment effect during the study. The fixed effects are period (baseline or treatment period), treatment, period-by-treatment interaction and circumcision status and the random effects are site and subject within site. From this model, the mean difference between PSD502 and placebo in the change from baseline will be estimated and the corresponding 95% confidence interval calculated.

Further analyses as suggested by the data may also be undertaken.

#### **5.2.3.9 Psychometric Analyses**

##### Primary objective

The evaluation of test-retest reliability will be made using the intra-class correlation coefficient (ICC) using a two-way mixed effect model with absolute agreement for single

measures. These analyses will be conducted using one pair of successive valid diary entries per subject where subject indicated no change from the PGI-S on the second sexual encounter. The primary analysis will use diary entries for sexual encounter 1 and sexual encounter 2. If the subject indicates having a change between sexual encounter 1 and sexual encounter 2, then that subject's diary entries for sexual encounter 2 and sexual encounter 3 will be used for the analysis; or if there is a change between 2 and 3, then diary entries for sexual encounter 3 and sexual encounter 4 will be used.

Convergent validity (demonstrating that different measures of the same concept substantially correlate when assessed concurrently) will be evaluated by examining magnitude of correlations between the PEBEQ Item 3 (event-specific bother) and the Independent NRS bother item. Convergent validity would be supported when the PEBEQ Item 3 (event-specific bother) are substantially correlated ( $\geq 0.40$ ).

Known-groups validity (the extent to which scores from a measure can discriminate between groups of participants that differ on a known relevant dimension, such as a measure/assessment of disease severity will be examined using an analysis of variance (ANOVA) model to ensure adequate variability in the bother grouping variables based on (1) IEQI, (2) PGI-S and (3) groups defined by the IELT  $\leq 30$  seconds,  $>30$  seconds- $\leq 1$  minute,  $>1$  minute- $\leq 2$  minutes, and  $>2$  minutes).

Responsiveness to change of the PEBEQ Item 3 (event-specific bother) will be examined between the mean response over the treatment period and the mean response during the baseline period. Effect size estimate of change ( $[\text{Mean}_{\text{treatment period}} - \text{Mean}_{\text{baseline}}] \div \text{standard deviation (SD)}_{\text{baseline}}$ ), standardized response mean ( $[\text{Mean}_{\text{treatment period}} - \text{Mean}_{\text{baseline}}] \div \text{SD}_{\text{change}}$ ), standardized mean change difference ( $[\text{Mean change}_{\text{PSD502}} - \text{Mean change}_{\text{placebo}}] \div \text{SD}_{\text{baseline pooled}}$ ), and Guyatt's statistic ( $[\text{Mean}_{\text{improved/worsened group in treatment period}} - \text{Mean}_{\text{improved/worsened group at baseline}}] \div \text{SD}_{\text{change in stable group}}$ ) will be used in the evaluation of responsiveness. For each type of effect size, a larger absolute value always indicates a stronger effect. Cohen (1988) defines effect sizes as: small (0.20), medium (0.50) and large (0.80).

Anchor-based assessments of change will also be evaluated. Differences in the PGI-S and IELT will be used to define subjects as responders (decrease in severity at end of study versus those that did not change or worsened at end of study) and descriptively compared to changes in PEBEQ Item 3 (event-specific bother). Similar analyses will be performed with PGI-S replaced with the other anchor scales.

To evaluate the consistency of effects across the entire distribution, a cumulative distribution plot (based on the cumulative distribution function [CDF]) will be generated showing the change from baseline by cumulative percent of subjects. This distribution curve will reveal the extent to which overall results are driven by outliers who improve or worsen more than others.

### ***5.2.3.10 Safety Analysis***

#### ***Study drug exposure***

The length of exposure and number of doses of study drug used during the treatment period will be summarized descriptively.

#### ***Adverse events***

The incidence of AEs occurring during the treatment period will be summarized by preferred term and body system for each treatment group. Similar summaries will be performed for treatment-related AEs, severe AEs, SAEs and AEs that lead to withdrawal.

The incidence of treatment-related AEs starting on the same day or the day after use of the study spray will also be summarized by body system and preferred term for each treatment group.

Adverse events reported by the subjects' partners will be listed and summarized descriptively as for the subject AEs.

#### ***Laboratory variables***

Absolute values and changes from baseline at the Final Evaluation Visit in laboratory measurements will be summarized for each treatment group.

#### ***Concomitant medications***

The incidence of concomitant medications taken during the treatment phase will be summarized for each treatment group.

#### ***Vital signs***

Absolute values and changes from baseline at the Final Evaluation Visit in vital signs measurements will be summarized for each treatment group.

#### ***Physical examination***

The number and percentage of subjects experiencing physical examination abnormalities will be summarized by treatment group.

#### ***12-lead electrocardiogram***

The number and percentage of subjects with abnormal ECG findings at the Final Evaluation Visit will be summarized for each treatment group.

#### ***Visual examination of the glans penis***

The number of subjects with abnormal findings on visual examination will be summarized for each treatment group.

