Subjects and their sexual partners will attend a Screening Visit (Visit 1) at which they will provide written informed consent. Subjects will be asked to complete a Subject Contact Form that collects the subject's preferred contact information for Plethora's selected vendor for qualitative interviews and the subjects will be screened for eligibility. The subject will be asked to answer a screening question on how bothered they are because of the quickness of their ejaculation on an 11-point NRS scale to confirm that they are bothered and will also be asked to complete the International Index of Erectile Function 5 (IIEF-5) questionnaire in order for the Investigator to assess erectile function. Screening will involve collection of demographic information, medical history (including history of PE), medication history, physical examination including visual examination of the glans penis, heart rate (HR), blood pressure (BP), 12-lead electrocardiogram (ECG) and blood sample collection (for hematology and biochemistry). As part of the screening procedures to confirm the subject's eligibility, the subject's sexual partner will undergo a urine pregnancy test at Visit 1. This result must be negative in order for the subject to participate in the study. Subjects that pass the initial screening assessments will then undergo a baseline evaluation period of 4 weeks during which they are required to have at least three sexual encounters. They will be provided with a stopwatch to measure IELT, a diary card in which to record adverse events (AEs), concomitant medications, date and time of sexual intercourse, PEBEQ responses, PGI-S, Independent NRS bother item, IEQI and IELT data after each encounter. They will also receive an electronic date and time stamper to document the time at which they record details for each sexual encounter in the diary card. Subjects will be instructed to start timing at vaginal penetration, stop timing at the start of ejaculation and that the diary must be completed immediately after the encounter if possible or within 12 hours of the encounter.

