Upon completion of the baseline period, subjects will return to the clinic for Visit 2. The diary card will be reviewed, and AE and concomitant medication information will be collected. Those subjects who have a baseline IELT of ≤ 1 minute for all sexual encounters, where each encounter is separated by at least 24 hours and who indicate a level of Bother on Item 3 of the PEBEQ of either "moderately", "quite a bit" or "extremely" on all encounters during the baseline period will be eligible to continue in the study and receive study medication for 4 weeks. Subjects will complete a baseline IPE questionnaire and also have their glans penis visually examined.

If the subject is eligible, he will be stratified into one of two groups, according to whether or not he is circumcised. The subject will be randomized within each stratification group to either PSD502 or placebo (1:1) and will be given sufficient study medication to last until the next clinic visit as well as a new diary card. The subject must be willing to use the study spray for all sexual encounters. The subject will be instructed on how to use the spray and instructed to use it in the next 4 weeks, at least once per week and to leave at least 24 hours between each sexual encounter. For each sexual encounter, the subject will time his IELT using a stopwatch. The subject will record the date and time of sexual intercourse, PEBEQ responses, PGI-S, Independent NRS bother item, IEQI, number of sprays used and IELT data in the diary card. The subject will document efficacy and tolerability data in a diary card and will use the date and time stamper to document the time at which they record details for each sexual encounter. The diary must be completed immediately after the encounter if possible or within 12 hours of the encounter.

At Visit 3, Final Evaluation Visit, the diary card, date and time stamper and any previously dispensed medication will be collected, AE and concomitant medication enquiries will be made and the subject will be asked to complete an IPE questionnaire. The subjects will undergo safety evaluations as for the Screening Visit (Visit 1), including examination of the glans penis. At this last visit, subjects will be asked to provide a PGI-C in the quickness of their ejaculation and will be asked to answer “Was this a meaningful or important change for you?” All subjects will also be asked to complete a PGI-C-Bother and will be asked if the change was meaningful or important.

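### The physical-examination, ECG and glans safety tables do not separate new findings from those present before treatment

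*SAP*

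**What the plan says.** SAP section 5.2.3.10 defines three categorical safety summaries.

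- Physical examination: "The number and percentage of subjects experiencing physical examination abnormalities will be summarized by treatment group". No visit is named.
- ECG: "The number and percentage of subjects with abnormal ECG findings at the Final Evaluation Visit will be summarized for each treatment group". The visit is fixed, but there is no reference to the earlier tracing.
- Glans: "The number of subjects with abnormal findings on visual examination will be summarized for each treatment group". No visit and no percentage are given.

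None of the three mentions baseline, change, shift, new onset or worsening.

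The continuous data in the same section are treated differently. For laboratory values the plan is "Absolute values and changes from baseline at the Final Evaluation Visit in laboratory measurements will be summarized for each treatment group", and the vital-signs paragraph follows the same pattern.

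The pre-treatment examinations exist. In the protocol synopsis (Methodology), the Screening Visit includes a physical examination, inspection of the glans and a 12-lead ECG. At Visit 2, where study medication is handed out, "Subjects will complete a baseline IPE questionnaire and also have their glans penis visually examined". At Visit 3, "The subjects will undergo safety evaluations as for the Screening Visit (Visit 1), including examination of the glans penis".

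**The concern.** The product is sprayed on the glans, and safety and tolerability is a stated secondary objective. The reader of the glans table will want to know how many men with a normal glans before treatment had an abnormal one afterwards, in each arm. A count of men with an abnormality does not answer that, because a man whose finding was noted at Screening or Visit 2 and has not changed adds one to his arm exactly as a man with a new finding does. The same holds for the ECG and the physical examination.

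The entry criteria do not rule out pre-existing findings. Exclusion criterion 4 removes a man with abnormal screening safety tests only when the investigator judges that they point to a condition precluding participation. Other abnormalities can be enrolled. At stake is the readability of three descriptive safety tables. No efficacy result depends on them.

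**Working it through.** **Denominator.** The plan states 50 per arm (SAP section 5.1), and this can be reproduced. For 20% versus 50%, two-sided 5% and 80% power, the uncorrected size is [1.960·√(2·0.35·0.65) + 0.842·√(0.16 + 0.25)]² / 0.30² = 38.5, or 39 per arm. The continuity correction, (38.5/4)·[1 + √(1 + 4/(38.5·0.30))]², raises this to 45. Allowing for 10% dropout, 45/0.90 = 50. So 50 per arm are randomized, and about 45 per arm have a Visit 3 examination if dropouts miss it.

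**Dilution.** Let b be the proportion with a pre-existing finding that persists to Visit 3, equal in both arms in expectation, and r the new-onset rate among the rest. The proportion counted as abnormal at Visit 3 is b + (1 − b)·r. The documents give neither b nor r. Purely as an illustration, take r = 10% on PSD502 and 2% on placebo, and let b run from 0 to 30%.

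| b | PSD502 counted | Placebo counted | Difference (points) | Ratio | Share of PSD502 count that pre-dates treatment, b/(b + (1 − b)·r) |
|---|---|---|---|---|---|
| 0% | 10.0% | 2.0% | 8.0 | 5.0 | 0% |
| 5% | 14.5% | 6.9% | 7.6 | 2.1 | 34% |
| 10% | 19.0% | 11.8% | 7.2 | 1.6 | 53% |
| 20% | 28.0% | 21.6% | 6.4 | 1.3 | 71% |
| 30% | 37.0% | 31.4% | 5.6 | 1.2 | 81% |

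Worked row, b = 10%: 0.10 + 0.90·0.10 = 0.190 and 0.10 + 0.90·0.02 = 0.118; 0.190/0.118 = 1.6; 0.10/0.190 = 53%.

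Counting new findings among men normal before treatment gives 10% versus 2%, ratio 5.0, at every b. The ratio is sensitive to b; the absolute difference moves much less, from 8.0 to 5.6 points.

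**What the new-onset count can say.** If no new finding is seen among n men normal before treatment, the exact two-sided 95% upper limit is 1 − 0.025^(1/n). With 45 examined per arm and none abnormal beforehand, n = 45 gives 7.9%. With 10% abnormal beforehand, n = 40 (45·0.90 = 40.5) gives 8.8%. With 30%, n = 31 (45·0.70 = 31.5) gives 11.2%. This is a usable safety statement that the planned tables do not provide.

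**Would tables by visit be enough?** Suppose an arm has five abnormal men before treatment and five at Visit 3. These may be the same five, with no new finding, or five resolved and five new. Separate counts by visit fit both cases; only a within-subject cross-tabulation distinguishes them.

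**The case against.** The strongest answer is the adverse event plan in the same section. It summarizes treatment-period AEs by arm, with further tables for treatment-related, severe and serious AEs and AEs leading to withdrawal. Another covers treatment-related AEs with onset on a day of spraying or the next day. A reader might infer from the examination tables that new local reactions are masked, or that the trial could not report how many men developed one. The documents do not support that. The AE tables are a separate route, and a better-timed one for short-lived reactions, because the glans is examined only once after treatment begins. What remains is that the available text does not say every new examination finding becomes an AE, and that the table tied to spray use also depends on a causality judgement.

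A reader might also infer that chance imbalance in pre-existing findings would drive the comparison between arms. That too goes further than the text allows. Randomization is 1:1, so such findings balance in expectation. They dilute the contrast rather than bias it systematically, and the safety analysis is descriptive. Chance imbalance at this size is possible, but its extent depends on an unknown prevalence.

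Three further points are fair. The ECG table is limited to the Final Evaluation Visit, so only persisting ECG findings enter it. The other two tables name no visit, and by-visit reporting would fit their wording. Change from baseline for continuous data does not contradict counts for categorical data; it shows only that a baseline reference was thought useful elsewhere in the section.

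Finally, sections 5.2.3 and 5.2.3.12 defer to a separate SAP to be finalized before database lock, and the sections before section 5 were not available for this check. Either could hold a baseline definition. The deferral itself supplies none.

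**Conclusion.** The point holds as a minor reporting weakness. As worded, the three tables do not distinguish new from pre-existing findings and so dilute a treatment-emergent signal, although the data to separate the two are collected.

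The size rests on assumptions. With new-onset rates of 10% and 2%, the ratio drops from 5.0 to between 2.1 and 1.2 for persisting baseline prevalences of 5% to 30%. No prevalence is documented for any of the three examinations, and that for the glans may be low: exclusion criterion 3 covers urological disease or genitourinary surgery within 8 weeks of Screening where it would prevent study procedures. If pre-existing findings are rare, the planned and the proposed tables nearly coincide. The primary analysis, the sample size and the AE tables are unaffected.

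**What to change.** In the physical-examination, ECG and glans paragraphs of SAP section 5.2.3.10, or in the separate SAP before database lock, add for each arm:

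1. A within-subject shift table, normal/abnormal at the last pre-treatment examination by normal/abnormal at Visit 3. The reference is Visit 2 for the glans and Screening for the ECG and physical examination. The denominator is safety-population subjects examined at both times.
2. The number and percentage with a new abnormality at Visit 3, with subjects normal before treatment and examined at both times as the denominator.
3. A separate listing of any pre-existing finding that worsened, since a normal/abnormal table cannot show worsening.

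The cost is a few sentences and some extra table rows. No new data, visits or procedures are needed.

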### ***5.2.3.11 Telephone Exit Interview***

Qualitative analysis on the telephone exit interview findings will be conducted by HRA.

#### ***5.2.3.12 Amendments to the Statistical Analysis***

Any changes to the planned statistical and/or psychometric analyses made prior to the database lock will be described in the SAP and/or PAP, along with the rationale for the changes, and noted in the final clinical study report.

Any changes made after database lock will be described in the final clinical study report, along with the rationale for the changes and a discussion of the potential biases in the analysis.

Statistical and psychometric analyses will be conducted according to separate plans (a SAP and PAP respectively) that will be finalized before the database is “locked”.
